6.6.2 Determination of drug concentration

Samples for determination of drug concentration in serum will be analysed by Quotient Bioresearch Ltd on behalf AstraZeneca, using an appropriate, validated, bioanalytical method. The method used will be an immunoassay using an anti-idiotypic antibody to tralokinumab to capture drug and an anti-human IgG₄ detection antibody. Full details of the analytical method used will be described in a separate bioanalytical report.

All placebo samples will be analysed.

6.7 Immunogenicity

Serum will be collected predose according to the schedule of study procedures to determine the immunogenicity of tralokinumab.

6.7.1 Collection of samples

Blood samples for determination of the immunogenicity of tralokinumab in serum will be taken at the times presented in the study plan Table 1. Whole blood is collected into serum gel tubes for serum preparation. The serum obtained from whole blood samples at each time point will be dispensed equally between the tubes specified for immunogenicity (approximately 0.25ml/tube).

Samples will be collected, labelled, stored, and shipped as detailed in Laboratory Manual. For blood volume see Section 7.1.

6.7.2 Immunogenicity analyses

The presence or absence of anti-tralokinumab antibodies will be determined in the serum samples at MedImmune Ltd., using an appropriate, qualified, bioanalytical method. The method used will be a homogeneous bridging immunoassay. Full details of the analytical method used will be described in a separate bioanalytical report.

All placebo samples will be analysed.

6.8 Pharmacogenetics

For details of procedure refer to Appendix D.

6.9 Pharmacogenomics and blood samples for exploratory analyses

Exploratory analyses on mRNA, cytokine levels including IL-13, periostin and other proteins will be evaluated to gain insight on the tralokinumab mechanism of action and the pathogenesis of UC.

6.9.1 Collection of samples

Blood samples for mRNA extraction and pharmacogenomic analyses, and blood samples for the determination of IL-13 and periostin in serum will be taken at the times presented in [Table 6](#).

Samples will be collected, labelled, stored and shipped as detailed in the Laboratory manual. For blood volumes, see Section [7.1](#).

7. BIOLOGICAL SAMPLING PROCEDURES

7.1 Volume of blood

The total volume of blood that will be drawn from each patient in this study is as follows:

Table 11 Volume of blood to be drawn from each patient

Assessment	Sample volume (mL)	No. of samples	Total volume (mL)	
Central Laboratory assessments				
Safety	Clinical chemistry	3.5	7	24.5
	Clinical chemistry (screening sample)	7	1	7
	Haematology	2	8	16
mRNA analysis	5	7	35	
Pharmacokinetic, Immunogenicity, Markers of Disease Activity and IL ¹	5	12	60	
Optional Pharmacogenetics ²	10	1	10	
Local Laboratory assessments				
TB screening	3	1	3	
Total			155.5	

¹ IL is intestinal leakiness

² Optional, only to be collected after patient has signed separate informed consent

Additional samples may be required if:

- an anaphylactic reaction occurs during or within a 24-hour period after administration of IP. The blood volume drawn for those assessments can be approximately 14ml.
- patient shows an AST **or** ALT $\geq 3 \times \text{ULN}$ **or** total bilirubin $\geq 2 \times \text{ULN}$ (refer to Appendix E). The blood volume can be at least approximately 12ml for first confirmation assessment.
- any of the other blood tests show abnormal results or give cause for concern.

7.2 Handling, storage and destruction of biological samples

The samples will be used up or disposed of after analyses or retained for further use as described here.

AstraZeneca will ensure all biological samples are returned to the source following the finalisation of the Clinical Study Report in all countries where it is a legal requirement.

7.2.1 Pharmacokinetic and immunogenicity samples

PK and immunogenicity samples will be retained for future use at MedImmune Ltd. or designee for a maximum of 25 years following the Last Subject's Last Visit. A summary of measured drug concentrations and immunogenicity results will be reported in the Clinical Study Report.

7.2.2 Biomarker samples

All blood, serum and plasma samples and all tissue biopsies collected to evaluate exploratory endpoints are considered biomarker samples.

AstraZeneca or a designee will retain key biological samples for investigation of the pharmacology of tralokinumab for a maximum of 25 years following the Last Subject's Last Visit. The results from the investigation of such samples will not be reported in the Clinical Study Report but in separate reports (e.g. bioanalytical, and biomarker reports) and in scientific publications as appropriate.

7.3 Labelling and shipment of biohazard samples

The Principal Investigator ensures that samples are labelled and shipped in accordance with the Laboratory Manual and the Biological Substance, Category B Regulations (materials containing or suspected to contain infectious substances that do not meet Category A criteria), see Appendix C 'IATA 6.2 Guidance Document'.

Any samples identified as Infectious Category A materials are not shipped and no further samples will be taken from the patient unless agreed with AstraZeneca and appropriate labelling, shipment and containment provisions are approved.

7.4 Chain of custody of biological samples

A full chain of custody is maintained for all samples throughout their lifecycle.

The Principal Investigator at each study site keeps full traceability of collected biological samples from the patients while in storage at the study site until shipment or disposal (where appropriate) and keeps documentation of receipt of arrival.

The sample receiver keeps full traceability of the samples while in storage and during use until used or disposed of or until further shipment and keeps documentation of receipt of arrival.

AstraZeneca keeps oversight of the entire life cycle through internal procedures, monitoring of study sites and auditing of external laboratory providers.

Samples retained for further use are registered in the AstraZeneca or designee biobank system during the entire life cycle.

7.5 Withdrawal of informed consent for donated biological samples

If a patient withdraws consent to the use of donated biological samples, the samples will be disposed of/destroyed, and the action documented. If samples are already analysed, AstraZeneca is not obliged to destroy the results of this research.

As collection of the biological samples is an integral part of the study, then the patient is withdrawn from further study participation.

As collection of the pharmacogenetic sample is optional and not an integral part of the study then the patient may continue in the study.

The Principal Investigator:

- Ensures patients' withdrawal of informed consent to the use of donated samples is notified immediately to AstraZeneca
- Ensures that biological samples from that patient, if stored at the study site, are immediately identified, disposed of /destroyed, and the action documented
- Ensures the laboratory(ies) holding the samples is/are informed about the withdrawn consent immediately and that samples are disposed/destroyed, the action documented and the signed document returned to the study site
- Ensures that the patient and AstraZeneca are informed about the sample disposal.

AstraZeneca ensures the central laboratory(ies) holding the samples is/are informed about the withdrawn consent immediately and that samples are disposed of/destroyed and the action documented and returned to the study site.

8. ETHICAL AND REGULATORY REQUIREMENTS

8.1 Ethical conduct of the study

The study will be performed in accordance with ethical principles that have their origin in the Declaration of Helsinki and are consistent with ICH/Good Clinical Practice, applicable regulatory requirements and the AstraZeneca policy on Bioethics and Human Biological Samples.

8.2 Patient data protection

The Informed Consent Form will incorporate (or, in some cases, be accompanied by a separate document incorporating) wording that complies with relevant data protection and privacy legislation.

8.3 Ethics and regulatory review

An Ethics Committee should approve the final study protocol, including the final version of the Informed Consent Form and any other written information and/or materials to be provided to the patients. The investigator will ensure the distribution of these documents to the applicable Ethics Committee, and to the study site staff.

The opinion of the Ethics Committee should be given in writing. The investigator should submit the written approval to AstraZeneca before enrolment of any patient into the study.

The Ethics Committee should approve all advertising used to recruit patients for the study.

AstraZeneca should approve any modifications to the Informed Consent Form that are needed to meet local requirements.

If required by local regulations, the protocol should be re-approved by the Ethics Committee annually.

Before enrolment of any patient into the study, the final study protocol, including the final version of the Informed Consent Form, is approved by the national regulatory authority or a notification to the national regulatory authority is done, according to local regulations.

AstraZeneca will handle the distribution of any of these documents to the national regulatory authorities.

AstraZeneca will provide Regulatory Authorities, Ethics Committees and Principal Investigators with safety updates/reports according to local requirements, including SUSARs (Suspected Unexpected Serious Adverse Reactions), where relevant.

8.4 Informed consent

The Principal Investigator(s) at each study site will:

- Ensure each patient is given full and adequate oral and written information about the nature, purpose, possible risk and benefit of the study
- Ensure each patient is notified that they are free to discontinue from the study at any time
- Ensure that each patient is given the opportunity to ask questions and allowed time to consider the information provided
- Ensure each patient provides signed and dated informed consent before conducting any procedure specifically for the study
- Ensure the original, signed Informed Consent Form(s) is/are stored in the Investigator's Study File
- Ensure a copy of the signed Informed Consent Form is given to the patient
- Ensure that any incentives for patients who participate in the study as well as any provisions for patients harmed as a consequence of study participation are described in the informed consent form that is approved by an Ethics Committee.

8.5 Changes to the protocol and informed consent form

Study procedures will not be changed without the mutual agreement of the International co-ordinating Investigator and AstraZeneca.

If there are any substantial changes to the study protocol, then these changes will be documented in a study protocol amendment and where required in a new version of the study protocol (Revised Clinical Study Protocol).

The amendment is to be approved by the relevant Ethics Committee and if applicable, also the national regulatory authority approval, before implementation. Local requirements are to be followed for revised protocols.

AstraZeneca will distribute any subsequent amendments and new versions of the protocol to each Principal Investigator(s). For distribution to Ethics Committee see Section [8.3](#).

If a protocol amendment requires a change to a study site's Informed Consent Form, AstraZeneca and the study site's Ethics Committee are to approve the revised Informed Consent Form before the revised form is used.

If local regulations require, any administrative change will be communicated to or approved by each Ethics Committee.

8.6 Audits and inspections

Authorised representatives of AstraZeneca, a regulatory authority, or an Ethics Committee may perform audits or inspections at the study site, including source data verification. The purpose of an audit or inspection is to systematically and independently examine all study-related activities and documents, to determine whether these activities were conducted, and data were recorded, analysed, and accurately reported according to the protocol, Good Clinical Practice (GCP), guidelines of the International Conference on Harmonisation (ICH), and any applicable regulatory requirements. The investigator will contact AstraZeneca immediately if contacted by a regulatory agency about an inspection at the study site.

9. STUDY MANAGEMENT BY ASTRAZENECA

9.1 Pre-study activities

Before the first patient is entered into the study, it is necessary for a representative of AstraZeneca to visit the investigational study site to:

- Determine the adequacy of the facilities
- Determine availability of appropriate patients for the study
- Discuss with the investigator(s) (and other staff involved with the study) their responsibilities with regard to protocol adherence, and the responsibilities of AstraZeneca or its representatives. This will be documented in a Clinical Study Agreement between AstraZeneca and the investigator.

9.2 Training of study site staff

Before the first patient is entered into the study, an AstraZeneca representative will review and discuss the requirements of the Clinical Study Protocol and related documents with the investigational staff and also train them in any study specific procedures and the WBDC system(s) utilised. AstraZeneca will provide training of study site staff during Investigator's Meeting and during Study Initiation Visits.

The Principal Investigator will ensure that appropriate training relevant to the study is given to all of these staff, and that any new information relevant to the performance of this study is forwarded to the staff involved. The Principal Investigator will maintain a record of all individuals involved in the study (medical, nursing and other staff).

9.3 Monitoring of the study

During the study, an AstraZeneca representative will have regular contacts with the study site, including visits to:

- Provide information and support to the investigator(s)

- Confirm that facilities remain acceptable
- Confirm that the investigational team is adhering to the protocol, that data are being accurately and timely recorded in the eCRFs, that biological samples are handled in accordance with the Laboratory Manual and that study drug accountability checks are being performed
- Perform source data verification (a comparison of the data in the eCRFs with the patient's medical records at the hospital or practice, and other records relevant to the study) including verification of informed consent of participating patients. This will require direct access to all original records for each patient (eg, clinic charts)
- Ensure withdrawal of informed consent to the use of the patient's biological samples is reported and biological samples are identified and disposed of/destroyed accordingly, and the action is documented, and reported to the patient.

The AstraZeneca representative will be available between visits if the investigator(s) or other staff at the study site needs information and advice about the study conduct.

9.3.1 Source data

Refer to the Clinical Study Agreement for location of source data.

9.4 Study agreements

The Principal Investigator at each study site should comply with all the terms, conditions, and obligations of the Clinical Study Agreement, or equivalent, for this study. In the event of any inconsistency between this Clinical Study Protocol and the Clinical Study Agreement, the terms of Clinical Study Protocol shall prevail with respect to the conduct of the study and the treatment of patients and in all other respects, not relating to study conduct or treatment of patients, the terms of the Clinical Study Agreement shall prevail.

Agreements between AstraZeneca and the Principal Investigator should be in place before any study-related procedures can take place, or patients are enrolled.

9.4.1 Archiving of study documents

The Investigator follows the principles outlined in the Clinical Study Agreement (CSA).

9.5 Study timetable and end of study

The end of the study is defined as 'the last visit of the last patient undergoing the study'.

The study is expected to start in Q1 and to end by Q1 .

The study may be terminated at individual study sites if the study procedures are not being performed according to GCP, or if recruitment is slow. AstraZeneca may also terminate the

entire study prematurely if concerns for safety arise within this study or in any other study with tralokinumab.

10. DATA MANAGEMENT BY ASTRAZENECA OR DELEGATE

Data management will be performed by AstraZeneca Data Management Centre staff.

Data will be entered in the Web Based Data Capture (WBDC) system at the study site. Trained study staff will be responsible for entering data on the observations, tests and assessments specified in the protocol into the WBDC system and according to the eCRF instructions. The eCRF instructions will also guide the study site in performing data entry. Data entered in the WBDC system will be immediately saved to a central database and changes tracked to provide an audit trail. The data will then be Source Data Verified (SDV), reviewed/ queried and updated as needed. The Principal Investigator is responsible for signing the eCRF and this can be delegated to a trained Investigator. The eCRF is signed electronically as per the eCRF instructions. The data will be validated as defined in the Data Management Plan.

Data queries will be raised for inconsistent, impossible or missing data. All entries to the study database will be available in an audit trail. Quality control procedures will be applied to each stage of data handling to ensure that all data are reliable and have been processed correctly.

The data will be frozen and then locked to prevent further editing. When all data have been coded, validated, signed and locked, clean file will be declared. Any treatment revealing data may thereafter be added and the final database will be locked. A copy of the eCRF will be archived at the study site when the study has been locked.

Management of external data

The data collected through third party sources will be obtained and reconciled against study data.

The Data Management Centre determines the format of the data to be received from external vendors and coordinates the flow of data to an external environment or clinical database (if applicable). Data Management will ensure that the data collection tool (eg, IVRS/IWRS etc) will be tested / validated as needed. External data reconciliation will be done with the clinical database as applicable.

Dictionary coding

Adverse events and medical/surgical history will be classified according to the terminology of the latest version the Medical Dictionary for Regulatory Activities (MedDRA). Medications will be classified according to the AstraZeneca Drug Dictionary. All coding will be performed by the Medical Coding Team at Data Management Centre.

Medical coding is done using the most current version of MedDRA and AstraZeneca Drug Dictionary.

Serious Adverse Event (SAE) Reconciliation

SAE Reconciliation Reports are produced and reconciled with Patient Safety database and/or the Investigational Site.

Data Management of genotype data

Refer to Appendix D.

Data associated with human biological samples

Data associated with biological samples will be transferred from laboratories internal or external to AstraZeneca.

11. EVALUATION AND CALCULATION OF VARIABLES BY ASTRAZENECA OR DELEGATE

11.1 Calculation or derivation of efficacy variable(s)

Calculation of efficacy variables will be performed by Cognizant.

Baseline is defined as the most recent measurement obtained before administration of IP. In most cases this will be data from randomisation visit (Visit 2), but if no such value exists, most recent value prior to Visit 2 will be used. Change from baseline for all variables will be calculated by subtracting the baseline value from the visit value. Variables analyzed on the logarithmic scale will be log-transformed before change from baseline is calculated.

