3.1.1 Study Periods

Enrolment period (E; Visit 1 – Visit 2, during week – 1)

The Enrolment Visit (Visit 1) will take place 2-7 days before the randomisation at Visit 2.

The purpose of the enrolment period is to ensure patient eligibility. Informed Consent will be obtained prior to conducting any study related assessments or activities. The patient will be assessed against inclusion and exclusion criteria applicable at Visit 1 (inclusion criteria 1, 2, 3, 5, 6, 7 and exclusion criteria 1, 2, 3, 4, 5, 6, 7, 8, 9, 10, 11, 12, 13, 14, 15, 18, 21, 22, 23, and 24).

Screening for tuberculosis will be performed according to local standard practice at each study site.

An endoscopy with biopsy sampling will be performed after the HIV, hepatitis B, hepatitis C and TB screening results have been reported negative, and before randomisation at Visit 2.

Patients will be instructed to monitor their symptoms of disease and record those in a Diary Card (see Section 6.1.1).

12-weeks Treatment Period: Randomisation (R, Visit 2, Week 0, DAY 1) and Treatment Visits (Visits 3 - 8)

Randomisation Visit and Visit 6 (week 8) will start with administration of the Ulcerative Colitis Global Health Question (UCGHQ) to the patient prior to any other assessments (see section 6.5.1).

On the Randomisation Visit assessment of eligibility criteria will continue. The patient will be assessed against inclusion and exclusion criteria applicable at randomisation (all inclusion and exclusion criteria except exclusion criterion 2).

If applicable, a blood sample for optional genetic research will be collected after signing of a separate Informed Consent.

Laboratory blood sampling including PK, ADA, biomarkers, and calprotectin in faeces will be done and shipped to a central laboratory. Pharmacokinetic (PK) samples should be collected before administration of IP. The exact timing of each sc injection and each PK sampling collection is to be recorded at each visit.

Eligible patients will be randomised to either tralokinumab (300mg) or placebo administered in 2 sc injections. An unblinded qualified designee, who is not involved in the management of the patients, will inject the investigational product into the sc tissue of the anterior thigh or abdomen. The site of injection will be assessed during all treatment visits (see Section [6.4.10.1](#)).

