6.3.3 Markers of Disease Activity and Intestinal Leakiness, and mRNA levels

The laboratory samples collected to measure mRNA levels, and to assess disease activity (CRP, periostin, cytokines and calprotectin) and intestinal leakiness (albumin) are displayed in [Table 8](#) by visit. These variables will be assessed at the central laboratories. For information on the collection, labelling, storage and shipment of samples, see the Laboratory Manual.

The faeces sample will consist of a dipstick rather than stool collection. Patients may collect the sample prior to the visit if properly trained in advance by site staff, but sample collection by site staff during the visit is preferred.

Table 8 Markers of Disease Activity and Intestinal Leakiness, and mRNA

VISIT	1	2	3	4	5	6	7	8	9	10	11
Week	-1	0	2	4	6	8	10	12	16	20	24
Albumin (serum)	X	X		X		X		X	X	X	X
CRP (serum)	X	X		X		X		X	X	X	X
Periostin (serum)		X		X		X		X	X	X	X
Cytokines (serum)		X		X		X		X	X	X	X
mRNA (blood)		X		X		X		X	X	X	X
Calprotectin (faeces)		X		X		X		X	X	X	X

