12.2.2.3 Change from baseline in partial Mayo score

Repeated measures analysis will be used to analyze the change from baseline in partial Mayo score. The model will include treatment, glucocorticosteroid-refractory status, partial Mayo score at baseline, visit, and treatment by visit interaction as explanatory variables. The contrasts of interest are the differences at each visit between tralokinumab and placebo. Depending on the distribution of the data, partial Mayo score will be treated as either a continuous or as an ordered categorical variable.

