12.2.2.4 Markers of disease activity (CRP, calprotectin) and intestinal leakiness (albumin)

Repeated measures analysis will be used to analyze the change from baseline in markers of disease activity and intestinal leakiness. The model will include treatment, baseline value, visit, and treatment by visit interaction as explanatory variables. The contrasts of interest are the differences at each visit between tralokinumab and placebo.

Markers of disease activity and intestinal leakiness will be log-transformed before analysis, unless otherwise is stated in the SAP. The number of CRP values below limit of quantification will be assessed before analysis to ensure the model appropriateness. In case of large number of values below limit of quantification another method of analysis should be considered for CRP, this method will be stated in the SAP.

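### CRP and albumin models could use the Visit 1 value and glucocorticosteroid-refractory status, both available before dosing, at almost no cost; the present plan is neither wrong nor biased

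*Protocol*

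**What the plan says.** - **Baseline (section 11.1).** "Baseline is defined as the most recent measurement obtained before administration of IP". This is normally Visit 2, and an earlier value enters only as a substitute: "if no such value exists, most recent value prior to Visit 2 will be used". Change from baseline is the visit value minus this baseline, on the log scale where a variable is log-transformed.
- **Sampling (section 6.3.3, Table 8).** Albumin and CRP are marked at Visits 1 and 2, then at weeks 4, 8, 12, 16, 20 and 24. Calprotectin is first marked at Visit 2. On where they are measured: "These variables will be assessed at the central laboratories".
- **Timing (section 3.1.1).** "The Enrolment Visit (Visit 1) will take place 2-7 days before the randomisation at Visit 2".
- **Marker model (section 12.2.2.4).** "The model will include treatment, baseline value, visit, and treatment by visit interaction as explanatory variables".
- **Partial Mayo model (section 12.2.2.3).** "The model will include treatment, glucocorticosteroid-refractory status, partial Mayo score at baseline, visit, and treatment by visit interaction as explanatory variables". The primary Cochran-Mantel-Haenszel test (12.2.1), mucosal healing and remission (12.2.2.1) and the Mayo model (12.2.2.2) also use refractory status.
- **What is left to the SAP.** Section 12.2.2.4 defers the log transformation, and a different CRP method if many values are below quantification. It does not defer the covariate list, and 11.1 does not defer the baseline rule.

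**The concern.** Two pre-dose values of CRP and albumin will exist for most patients, taken a few days apart and analysed centrally. The model conditions on one of them. A single value carries day-to-day and assay noise, and a second value taken before dosing may explain some of the follow-up variation that the first does not.

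Separately, the marker model has the same structure as the partial Mayo model except that refractory status is missing, and no reason is given. Section 5.2.1 names no stratification factor for randomisation, so with about 110 patients some chance imbalance on that status is possible.

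At stake is the width of the confidence intervals for the treatment contrasts on these markers, in a trial whose size was set by the binary primary endpoint alone.

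**Working it through.** **The plan's own figure.** The only design figure is 53 patients per arm (section 12.3), from 65% against 35%, one-sided 0.05 and 90% power. The normal-approximation formula gives 46 per arm, and 53 with continuity correction, so the figure reproduces. It concerns the primary endpoint only; 2 x 53 = 106 is used below as the analysed number. The protocol states no precision for the markers.

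**Assumed inputs.** The protocol gives neither correlations nor the prognostic strength of refractory status. Write r1 and r2 for the correlations of log Visit 1 and log Visit 2 with a follow-up value, and r12 for their correlation with each other. The calculation is for one follow-up visit.

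**Second baseline as an additional covariate.** With both values in the model, R² = (r1² + r2² - 2·r1·r2·r12)/(1 - r12²). The variance ratio against the current model is (1 - R²)/(1 - r2²), before any lost degree of freedom. When r1 = r2 = r, R² reduces to 2r²/(1 + r12).

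| r1 | r2 | r12 | Variance ratio | Standard error ratio |
|---|---|---|---|---|
| 0.5 | 0.5 | 0.8 | 0.963 | 0.981 |
| 0.5 | 0.5 | 0.9 | 0.983 | 0.991 |
| 0.7 | 0.7 | 0.8 | 0.893 | 0.945 |
| 0.7 | 0.7 | 0.9 | 0.949 | 0.974 |
| 0.45 | 0.5 | 0.8 | 0.991 | 0.995 |
| 0.40 | 0.5 | 0.8 | 1.000 | 1.000 |

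In the last row R² = (0.16 + 0.25 - 0.32)/0.36 = 0.25, which equals r2². Visit 1 then adds nothing and does no harm.

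**Why the mean should not replace Visit 2.** Section 11.1 takes change from Visit 2. With Visit 2 in the model, analysing that change or the raw follow-up value gives the same treatment contrast. If the covariate becomes the mean of the two visits while the outcome still subtracts Visit 2, the noise in Visit 2 is no longer fully absorbed. Under a common correlation ρ the ratio to the current model is 2/(1 + ρ) - (1 - ρ)/(2(1 + ρ)²):

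- ρ = 0.4: 1.429 - 0.153 = 1.28
- ρ = 0.5: 1.333 - 0.111 = 1.22

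Even with the raw follow-up value as outcome, the mean loses if Visit 1 predicts less well: r1 = 0.40, r2 = 0.50, r12 = 0.8 gives 1.033.

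**Refractory status.** One added term moves the residual degrees of freedom from 103 to 102 at N = 106, so the ratio is (1 - partial R²) x 103/102:

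- partial R² 0: 1.010
- 0.02: 0.990
- 0.05: 0.959
- 0.10: 0.909

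**Scale.** At r1 = r2 = 0.5, r12 = 0.8, 53 per arm, two-sided 5% and 80% power, the detectable difference falls from 0.471 to 0.463 standard deviations.

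**The case against.** The strongest reply is that nothing here is wrong. The most-recent-value rule is conventional, unambiguous and the same as for the safety variables in 11.2. With 1:1 randomisation it is unbiased. Marker models need not share covariates with Mayo models, and a SAP may refine secondary models. All of this stands, and it is why the point is only an optional improvement.

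Four stronger readings are tempting, and the protocol does not support them:

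- **That the Visit 1 value is thrown away.** It is kept as the fallback, and is unused only when a Visit 2 value exists.
- **That the gain is large.** A common correlation of 0.4 to 0.8 among all visits gives variance ratios of 0.918 to 0.803, which is like 9% to 25% more patients (1/0.918 = 1.09; 1/0.803 = 1.25). That assumes samples 2 to 7 days apart correlate no more closely than samples weeks apart, and the protocol gives no ground for it.
- **That omitting refractory status widens every contrast.** It does so only if the status predicts a marker beyond that marker's own baseline, and no evidence is given.
- **That bowel preparation or biopsy disturbs the Visit 2 sample.** Nothing in the protocol says these procedures alter CRP or albumin, and the order of endoscopy and blood sampling is not fixed.

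**Conclusion.** A small efficiency gain is available on secondary markers, together with an unexplained difference in covariates between 12.2.2.3 and 12.2.2.4. There is no bias, and the primary analysis and sample size are untouched.

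For CRP and albumin, a second baseline covariate lowers residual variance by about 2% to 11% if both visits predict follow-up equally (r 0.5 to 0.7, r12 0.8 to 0.9), falling to zero as Visit 1 becomes redundant. Calprotectin cannot gain from this part. Adding refractory status changes variance by +1% to -9% for partial R-squared 0 to 0.10. The worst case is one degree of freedom per added term, about 1% of variance each.

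All these sizes rest on assumed correlations and on a single-visit calculation. A repeated-measures model with one baseline slope for all visits may gain somewhat less at a given visit.

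**What to change.** 1. Leave section 11.1 as it is: Visit 2 remains the baseline for the change score.
2. In 12.2.2.4, add glucocorticosteroid-refractory status as a factor for CRP, calprotectin and albumin, or state why it is left out.
3. For CRP and albumin, enter log Visit 1 as a second covariate beside log Visit 2. Do not put their mean in place of Visit 2.
4. Prespecify a simple rule for a missing value, for example that the available pre-dose value stands in for the missing one in both covariates. Handle CRP values below quantification in the same way at both visits.
5. Calprotectin keeps its single baseline.

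The cost is a few lines of text, settled before clean file is declared, with no new samples or procedures. Statistically it is one degree of freedom for calprotectin and two each for CRP and albumin.
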